### 4.3 Exclusion Criteria

An adult who meets any of the following exclusion criteria at screening will not be eligible for randomization in the study:

1. Use of any investigational medicinal product within 90 days prior to randomization or planned use of such a product during the period of study participation.
2. Adults who have previously been vaccinated against *S. pneumoniae*.
3. History of microbiologically confirmed invasive disease caused by *S. pneumoniae*.
4. History of allergic disease (including angioedema) or history of a serious reaction to any prior vaccination or known hypersensitivity to any component of the study vaccines, including PEG.
5. Any abnormal vital sign deemed clinically relevant by the PI.
6. Acute illness at time of randomization (moderate or severe) and/or fever (body temperature of  $\geq 38.0^{\circ}\text{C}$ ) see note below.
  - a. Note: A minimum of 48 hours following a documented fever must pass before the participant can be vaccinated.
7. History of any non-study vaccine administration within 14 days of study vaccine administration.
8. No planned vaccines until after Day 29 (Visit 3).
9. Chronic administration (defined as more than 14 consecutive days) of immunosuppressant or other immune modifying drugs prior to the administration of the study vaccine (and within the 6 months prior to administration of the study vaccine), including the use of glucocorticoids. The use of topical and inhaled glucocorticoids will be permitted.
10. Administration of immunoglobulins and/or any blood products within the 6 months prior to administration of the study vaccine or anticipation of such administration during the study period.
11. Any medical or social condition that in the opinion of the PI\*, may interfere with the study objectives, pose a risk to the participant, or prevent the participant from completing the study follow-up.
12. Any screening laboratory test result outside the normal range and with toxicity score  $\geq 2$ , unless allowed by the PI, IVT Chief Medical Officer (CMO), and PATH Medical Officer (MO). A participant may repeat each laboratory assessment once during the screening period, with the most recent laboratory value being used for evaluation of exclusion criteria.
13. A positive serologic test for human immunodeficiency virus (HIV)-1 or HIV-2 (HIV 1/2 Ab), hepatitis B (HBsAg) or hepatitis C (HCV Ab).

\* The term "PI" is used throughout this protocol to refer to either the PI or designee.

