4.6.5 Analysis of Primary Objective

All safety analyses will be conducted in the safety analysis population, according to the treatment received. Frequencies and percentages of participants with any solicited AE, solicited local AE, solicited systemic AE, unsolicited AE, clinical safety laboratory abnormality, SAE will be tabulated along with an exact two-sided 95% CI computed via the Clopper-Pearson method. The denominators for percentages

will be the number of participants with the data available for analysis for the given endpoint. Participant-level data listing will be provided.

Solicited local and systemic AEs: All solicited AEs reported during 7 days post vaccination will be summarized according to defined severity grading scales. Frequencies and percentages of participants experiencing each solicited AE will be presented by treatment group and severity.

Hematological and biochemical measurements: For clinical safety laboratory data collected at screening and 7 days post-vaccination, individual Hgb, WBC count, Plts, AST, ALT, and creatinine values will be graded according to Table 10 and summarized by toxicity grading and study group. In addition, summaries of changes from baseline will be presented. Clinically significant laboratory abnormalities will be considered an AE and relatedness will be reported.

Unsolicited AEs: All unsolicited AEs with onset occurring during the first 28 days post vaccination will be assessed for severity and relatedness to study product by the PI. Frequencies and percentages of participants with unsolicited AEs will be summarized by the SOC, PT, and treatment group. Similar summaries will be provided for severity and relatedness of the unsolicited AEs.

SAEs: All SAEs through Visit 4 (Day 169) will be recorded and summarized. Frequencies and percentages of participants with SAEs and relatedness to study vaccine of the events will be summarized by SOC, PT, and treatment group.

When an AE occurs more than once for a participant, the participant will be only counted once for the corresponding PT according to the maximum severity of the events. A summary table will be prepared for unsolicited AEs comprised of the following categories:

- Unsolicited AEs
- Related unsolicited AEs
- SAEs
- Related SAEs
- SAEs leading to death
- Unsolicited AEs leading to participant discontinuation

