5.2 Pause Rules

The DSMB will be convened if any of the following study pause rules are met during the conduct of the trial:

- Rule 1: 1 or more participant experiences any vaccine-related Grade 4 AE or any vaccine-related SAE.
- Rule 2: 1 or more participant experiences Grade 3 or greater local reaction classified as related to vaccination by the PI: ulceration, necrosis, or sterile abscess at the injection site requiring drainage or surgical intervention.
- Rule 3: ≥ 5 participants in the same group inclusive of participants from Groups A, B, C, and D that experience the same Grade 3 (or greater) AE or laboratory abnormality attributed (related) to study vaccine. In the case of fever and pain at the injection site, the episode must last longer than 48 hours, and, in the case of fever, be confirmed by the PI without evidence of other medical causes.

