5.4 Serum and Hematology Toxicity

Table 10: Serum and Hematology Toxicity Grading

Serum	Mild (Grade 1)	Moderate (Grade 2)	Severe (Grade 3)	Potentially Life Threatening (Grade 4)
Creatinine (mg/dL)	1.1 – 1.3 x ULN	>1.3 – 1.8 x ULN OR increase of >0.3 above baseline	>1.8 – <3.5 x ULN OR increase of 1.5 – <2.0 x above baseline	≥3 .5 x ULN OR increase of >2.0 x above baseline
Liver function tests – AST, ALT increased	1.25 – <2.5 x ULN	2.5 – <5.0 x ULN	5.0 – <10.0 x ULN	≥10.0 x ULN
Hematology	Mild (Grade 1)	Moderate (Grade 2)	Severe (Grade 3)	Potentially Life Threatening (Grade 4)
Hemoglobin [Female] (g/dL)	11.0 – 12.0	9.5 – 10.9	8.0 – 9.4	< 8.0
Hemoglobin [Male] (g/dL)	12.5 – 13.5	10.5 – 12.4	8.5 – 10.4	< 8.5
OR decrease Hemoglobin, change from baseline value (g/dL)	1.0 – 1.5	1.6 – 2.0	2.1 – 5.0	> 5.0
WBC, increased (cell/mm ³)	10,800 – 15,000	15,001 – 20,000	20,0001 – 25,000	> 25,0000
WBC, decreased (cell/mm ³)	2,500 – 3,400	1,500 – 2,499	1,000 – 1,499	< 1,000
Platelets, decreased (cell/mm ³)	100,000 – <125,000	50,000 – <100,000	25,000 – < 50,000	< 25,000

Abbreviation: ULN = upper limit of normal range

Note: the laboratory values provided in this table serve as guidelines and are dependent upon institutional normal parameters.

Note: the severity grading scales used in this study are derived in part from *Guidance for Industry, Toxicity Grading Scale for Healthy Adult and Adolescent Volunteers Enrolled in Preventive Vaccine Clinical Trials*, U.S. Department of Health and Human Services, FDA, CBER, September 2007, and the *Division of AIDS (DAIDS) Table for Grading the Severity of Adult and Pediatric Adverse Events* (Version 2.1, July 2017), US National Institutes of Health.

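### As printed in both documents, the raised-WBC row of the laboratory grading table has an empty Grade 3 and leaves every value from 20,001 to 250,000/mm³ without a grade

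*SAP*

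**What the plan says.** SAP 4.6.5 (Analysis of Primary Objective) covers the screening and Day 8 safety laboratory results. It says that "WBC count, Plts, AST, ALT, and creatinine values will be graded according to Table 10 and summarized by toxicity grading and study group".

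Table 10 is in SAP 5.4, and Protocol Appendix 4 prints the same WBC digits. For raised WBC (cells/mm³) both give:

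| Grade | As printed |
|---|---|
| 1 | 10,800 – 15,000 |
| 2 | 15,001 – 20,000 |
| 3 | 20,0001 – 25,000 |
| 4 | > 25,0000 |

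A note under the table adds that "the laboratory values provided in this table serve as guidelines and are dependent upon institutional normal parameters".

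The grades are used in two further places:

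- Pause Rule 3 (SAP 5.2, Protocol 9.2) is met when at least five participants in the same group "experience the same Grade 3 (or greater) AE or laboratory abnormality attributed (related) to study vaccine".
- Exclusion 12 (Protocol 4.3) begins "Any screening laboratory test result outside the normal range and with toxicity score" and sets the score at 2 or more, with a possible allowance by the PI and two medical officers. Protocol 6.2.1 repeats this and points to Appendix 4.

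In the creatinine row, the change-from-baseline limits are 1.5 to <2.0 x for Grade 3 and >2.0 x for Grade 4. A rise of more than 0.3 above baseline is Grade 2.

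**The concern.** A severity scale should give every abnormal value exactly one grade, rising with the value. The raised-WBC row does not. Its Grade 3 lower limit is larger than its upper limit, and its Grade 4 limit is ten times the upper limit printed for Grade 3.

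The same digits stand in two separate documents, so a fault in reading the PDF is unlikely. No other section corrects them or supplies another WBC scale.

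Three uses are affected:

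- The graded laboratory table, part of the primary safety analysis, would show no raised-WBC result as Grade 3 and almost none as Grade 4.
- The laboratory part of Pause Rule 3 could be reached by a raised WBC only above 250,000.
- At screening, a WBC of 22,000 would have no toxicity score for exclusion 12, while 18,000 would score 2.

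**Working it through.** **Inputs.** The four printed bands above, from SAP Table 10 and Protocol Appendix 4, with commas removed and read as whole numbers. No sample-size or power figure is involved.

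**Step 1, as printed.**

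- Grade 2 ends at 20,000.
- Grade 3 requires 200,001 ≤ WBC ≤ 25,000. Since 200,001 > 25,000, no value qualifies.
- Grade 4 requires WBC > 250,000.
- The ungraded range is therefore 20,001 to 250,000, which is 250,000 − 20,001 + 1 = 230,000 consecutive whole-number values.

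**Step 2, one surplus zero dropped from each number.** This is an assumption, used only to test whether a typing slip explains the gap. Grade 3 becomes 20,001 to 25,000 and Grade 4 becomes above 25,000. No value from 10,800 upward is then ungraded.

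| WBC (cells/mm³) | As printed | Surplus zeros dropped (assumption) |
|---|---|---|
| 18,000 | 2 | 2 |
| 20,001 | none | 3 |
| 22,000 | none | 3 |
| 25,001 | none | 4 |
| 100,000 | none | 4 |
| 250,000 | none | 4 |
| 250,001 | 4 | 4 |

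**Step 3, both numbers matter.** Under the same assumption, repairing only Grade 3 leaves 25,001 to 250,000 ungraded (225,000 values). Repairing only Grade 4 leaves 20,001 to 25,000 ungraded (5,000 values).

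**Step 4, dependence on coding.** A program that tests both ends of each band gives no grade from 20,001 to 250,000. One that uses only the lower limits would give Grade 2 from 20,001 to 200,000 and Grade 3 from 200,001 to 250,000. Under either, 22,000 does not reach Grade 3. Under the second it would still score 2 for exclusion 12.

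**Step 5, creatinine.** Read the change limits as the ratio of the new value to baseline *b*. A ratio of exactly 2.0 is not below 2.0, so it is not Grade 3, and not above 2.0, so it is not Grade 4. The rise is 2.0*b* − *b* = *b*, which exceeds 0.3 whenever *b* > 0.3 mg/dL, so Grade 2 applies. A ratio of 1.9 is Grade 3. The value at 2.0 x thus ranks below the one at 1.9 x, unless it also exceeds 1.8 x ULN and is graded higher on that limb.

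**The case against.** The strongest reply is that this is an obvious slip. Neither malformed number is validly grouped, the adjoining limits show the likely intent, and a band whose lower limit exceeds its upper limit would probably stop a careful programmer. Nothing in the documents shows that any value was misgraded. This stands as a limit on the consequence. It does not repair the table, because an approved SAP should not leave its cut-offs to be inferred.

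The table note calls the values guidelines tied to institutional normal parameters. It gives no alternative Grade 3 or Grade 4 limits, and SAP 4.6.5 applies the table as the grading rule.

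It is also true that high values stay visible. SAP 4.6.5 keeps participant listings, change-from-baseline summaries and the reporting of clinically significant abnormalities as AEs. Protocol 11.5.5 also counts participants outside the normal range, although SAP 4.6.5 does not carry that wording over. Pause Rule 3 needs five related cases in one group and has an AE route as well. Exclusion 12 allows an override, and exclusion 11 rests on the PI's judgement. All of this stands.

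A reader might infer that Pause Rule 1 is disabled too. The documents do not support that. Rule 1 concerns vaccine-related Grade 4 AEs and related SAEs, and unsolicited AEs are graded on the functional scale in Protocol Table 11, so a marked leukocytosis can reach Rule 1 whatever the WBC row says.

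**Conclusion.** The raised-WBC row is wrong as written in both documents and should be corrected. On a literal reading Grade 3 is empty and 20,001 to 250,000/mm³ has no grade. The graded laboratory summary, the laboratory part of Pause Rule 3 and exclusion 12 all depend on it.

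The practical effect is limited. It arises only if the printed limits are used for grading, it concerns values that should be rare in healthy adults, and those values remain visible elsewhere in the safety reporting.

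Three stronger readings should be avoided:

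- The scale is not reversed. It has a gap between Grade 2 and Grade 4.
- Not every extreme value loses its grade, since values above 250,000 are Grade 4 as printed.
- A creatinine rise of exactly 2.0 x is normally not ungraded. It usually meets Grade 2, and the fault is that it ranks below a smaller rise. This is a single boundary point and secondary.

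That one surplus zero was typed in each WBC number is an inference from the adjoining bands. Only the sponsor can confirm the intended limits.

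**What to change.** The sponsor should:

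1. Confirm the intended Grade 3 and Grade 4 limits for raised WBC. Then correct the row in SAP Table 10 and Protocol Appendix 4 together, so that the grades are contiguous and consistent with the adjoining bands.
2. Assign the exact 2.0 x creatinine boundary to one grade in both tables.
3. Check that the grading program and the data-entry edit checks use the corrected table. If the printed limits were used, re-run the grading of the screening and Day 8 values.

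The cost is one table row and one boundary in two documents, plus a program check. No new data are needed.

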4.6.6 Analysis of Secondary Objective

The analysis of immunogenicity will be performed on the PP population as the primary analysis and the full analysis population as a secondary analysis.

Immunogenicity data will be descriptively analyzed. Serotype-specific IgG antibody responses will be measured at baseline (V1), and 28 days after study vaccination (V3).

- GMC with two-sided 95% CIs
- GMFR from baseline with two-sided 95% CI
- Percentage of participants achieving a ≥ 4 -fold IgG rise from baseline to Day 29 after vaccination by group with two-sided Clopper-Pearson 95% CI

Serotype-specific functional antibody responses will be measured by OPA and summarized at baseline (V1) and 28 days after study vaccination (V3),

- GMTs with two-sided 95% CIs,
- GMFR from baseline with 95% CI

GMCs and GMTs will be calculated for each treatment group along with their two-sided 95% CI, by exponentiating the corresponding log-transformed mean and their two-sided 95% confidence limits.

The ratio of the GMC/GMT between IVT PCV-25 formulations [REDACTED] to Prevnar 20TM and corresponding two-sided 95% CI will be provided. The log-transformed antibody responses will be used to construct a mean difference between the treatment groups and the comparator vaccine, Prevnar 20TM and its two-sided 95% CI using the two-sample t-test method. The mean difference and corresponding 95% CI will be back-transformed to obtain the GMC/GMT ratio between the two groups and corresponding 95% CI.

An adjusted GMC/GMT ratio between the treatment groups will be also provided along with its two-sided 95% CI. The log-transformed antibody responses will be used to compute a mean difference between each of the IVT PCV-25 groups and the Prevnar 20 group, along with corresponding two-sided 95% CIs, using analysis of covariance (ANCOVA) with log-transformed baseline antibody responses as a covariate. Other variables, such as age and sex, will be evaluated for inclusion in the ANCOVA model as well, using stepwise selection method. The mean difference and its 95% CI will be exponentiated to obtain the adjusted GMC/GMT ratio between the two groups and corresponding 95% CI.

GMFRs and corresponding two-sided 95% CIs will be computed for each treatment group. The mean difference in the log-transformed antibody responses between 28 days post vaccination and baseline and corresponding two-sided 95% CI will be calculated using the paired t-test method and then back-transformed to obtain GMFR and its 95% CI. The two-sample t-test method will be used to obtain the two-sided 95% CI of the ratio of GMFRs between the study groups. The distribution of concentrations/titers will be summarized using reverse cumulative distribution (RCD) curves at applicable time points. Forest plots will be created to visualize the IgG and OPA GMRs at 28 days post-vaccination. The distribution of antibody concentrations/titers at baseline and 28 days post-vaccination, as well as their fold-rises at 28 days post-vaccination, will be summarized using box plots.

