### 11.5.6 Analysis of Secondary Objectives

The analysis of immunogenicity will be performed on the PP population as the primary analysis and the full analysis population as a secondary analysis.

Immunogenicity data will be descriptively analyzed. Serotype-specific IgG antibody responses will be measured at baseline (V1), and 28 days after study vaccination (V3).

- GMC with two-sided 95% CIs
- GMFR from baseline with two-sided 95% CI

Serotype-specific functional antibody responses will be measured by OPA and summarized at baseline (V1) and 28 days after study vaccination (V3),

- GMTs with two-sided 95% CIs,
- GMFR from baseline with 95% CI

GMCs and GMTs will be calculated for each treatment group along with their two-sided 95% CI, by exponentiating the corresponding log-transformed mean and their two-sided 95% confidence limits.

The ratio of the GMC/GMT between IVT PCV-25 formulations [REDACTED] to Prevnar 20™ and corresponding two-sided 95% CI will be provided. The log-transformed antibody responses will be used to construct a mean difference between the treatment groups and the comparator vaccine, Prevnar 20™ and its two-sided 95% CI using the two-sample t-test method. The mean difference and corresponding 95% CI will be back-transformed to obtain the GMC/GMT ratio between the two groups and corresponding 95% CI. An adjusted GMC/GMT ratio between the treatment groups will be also provided along with its two-sided 95% CI. The log-transformed antibody responses will be used to compute a mean difference between the two groups and corresponding two-sided 95% CI using analysis of covariance (ANCOVA) with log-transformed baseline antibody responses as a covariate. Other variables, such as age and sex, will be evaluated for inclusion in the ANCOVA model as well. The mean difference and its 95% CI will be exponentiated to obtain the adjusted GMC/GMT ratio between the two groups and corresponding 95% CI.

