4.1 Overview

This is a multicenter, randomized, active-controlled, observer-blind Phase 2 trial in 220 healthy adults (age 18-49 years) residing in Canada. Eligible participants will be randomized to four groups as shown below (Table 3) in a 2:3:4:2 ratio.

No formal statistical hypothesis tests between treatment groups are planned in this study. All analyses for safety and immunogenicity data will be descriptive. When appropriate, continuous data will be summarized using descriptive statistics such as number of subjects with non-missing values, mean, standard deviation (SD), median, minimum, and maximum. Categorical data will be presented using the percentage of subjects in each category. A two-sided 95% CI will be provided for estimates, as appropriate. Individual subject data will be provided in listings. All statistical analyses will be performed using SAS® software Version 9.4 or later. Subject-wise data listings will be provided.

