		1.0	0.49-2.03	0.53-1.87	0.56-1.79
	0.45	0.5	0.24-1.05	0.26-0.97	0.27-0.94
		0.75	0.36-1.58	0.38-1.46	0.40-1.41
		1.0	0.48-2.10	0.51-1.95	0.53-1.88
	0.50	0.5	0.23-1.09	0.25-1.02	0.25-0.98
		0.75	0.34-1.64	0.37-1.53	0.38-1.47
		1.0	0.46-2.18	0.49-2.03	0.51-1.96
0.6	0.50	0.5	0.21-1.18	0.23-1.08	0.24-1.03
		0.75	0.32-1.78	0.35-1.62	0.37-1.54
		1.0	0.42-2.37	0.46-2.15	0.49-2.05
	0.55	0.5	0.20-1.23	0.22-1.12	0.23-1.07
		0.75	0.31-1.84	0.33-1.68	0.35-1.61
		1.0	0.41-2.45	0.45-2.25	0.47-2.15
	0.60	0.5	0.20-1.27	0.21-1.17	0.22-1.12
		0.75	0.29-1.91	0.32-1.76	0.33-1.69
		1.0	0.39-2.55	0.43-2.34	0.44-2.25

Note: CI = confidence interval; N₁ is the sample size in the IVT PCV-25 group; N₂ is the sample size in the Prevnar

20 group. An attrition rate of 10% was used in calculating the expected 95% CIs.

If the true SD of \log_{10} antibody concentrations for a specific serotype is 0.5 in the IVT PCV-25 group and 0.45 in the Prevnar 20 group and the true GMC ratio between the two groups is 0.75, the expected two-sided 95% CI for the GMC ratio between the two groups is (0.36, 1.58) with 18 evaluable participants per group, (0.38, 1.46) with 27 evaluable participants in the IVT PCV-25 group and 18 evaluable participants in the Prevnar group, and (0.40, 1.41) with 36 evaluable participants in the IVT PCV-25 group and 18 evaluable participants in the Prevnar group.

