4.7 Multiplicity

Due to the descriptive and exploratory nature of the analyses, no adjustment for multiplicity will be performed.

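### Stepwise covariate selection from an open list leaves the adjusted GMC/GMT model unfixed across serotypes, assays and analyses; the loss of CI coverage is slight, and a fixed covariate list removes the problem

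*SAP*

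**What the plan says.** SAP section 4.6.6 plans two versions of each GMC/GMT ratio against Prevnar 20.

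- **Unadjusted:** a mean difference in log response, with "its two-sided 95% CI using the two-sample t-test method".
- **Adjusted:** "An adjusted GMC/GMT ratio between the treatment groups will be also provided along with its two-sided 95% CI", obtained "using analysis of covariance (ANCOVA) with log-transformed baseline antibody responses as a covariate". The section then adds: "Other variables, such as age and sex, will be evaluated for inclusion in the ANCOVA model as well, using stepwise selection method".

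Protocol section 11.5.6 has the same open list but names no selection method: "Other variables, such as age and sex, will be evaluated for inclusion in the ANCOVA model as well". Protocol section 11.5.3 leaves the detailed analyses to a SAP finalised before the interim analysis, so the SAP is where the model should be settled.

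The SAP does not give a closed list of candidates or an entry or stay criterion. It does not say whether selection is done once or repeated by outcome. It also does not say whether the forest plots in section 4.6.6 show the unadjusted or the adjusted ratio. On the general framework it states "No formal statistical hypothesis tests between treatment groups are planned in this study" (section 4.1) and "no adjustment for multiplicity will be performed" (section 4.7).

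**The concern.** Stepwise selection uses the outcome data to choose the model, and the CI from the chosen model is then calculated as if the model had been fixed beforehand. With no closed list and no criterion, two programmers following section 4.6.6 could produce different adjusted ratios from the same data.

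The number of fits makes this matter. There are 26 serotypes and two assays, so 52 outcomes and 52 × 3 = 156 formulation-versus-comparator ratios per population. IgG is analysed at the interim and again at the final analysis. If selection is repeated each time, a serotype's adjusted ratio can move between analyses partly because the covariates changed.

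The ratios have a use beyond description. The Study Design part of the protocol summary says that the first analysis serves to exclude formulations that are clearly insufficiently immunogenic. By the final analysis the sponsor will have seen group-level IgG and OPA results, so a model still open at that stage invites questions that a fixed one would not.

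**Working it through.** **1. The plan's own precision figure.** SAP section 4.3 takes SDs of log10 concentration of "0.5 in the IVT PCV-25 group and 0.45 in the Prevnar 20 group", a true ratio of 0.75 and 10% attrition. The interval is 10^(log10 0.75 ± t × SE), with SE = √(0.5²/n₁ + 0.45²/n₂) and Satterthwaite degrees of freedom.

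| Evaluable | SE | df | t | Half-width | Computed CI | SAP |
|---|---|---|---|---|---|---|
| 18:18 | 0.1586 | 33.6 | 2.033 | 0.3223 | 0.357–1.575 | 0.36–1.58 |
| 27:18 | 0.1432 | 39.2 | 2.022 | 0.2896 | 0.385–1.461 | 0.38–1.46 |
| 36:18 | 0.1349 | 37.5 | 2.025 | 0.2732 | 0.400–1.407 | 0.40–1.41 |

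The SAP figures are reproduced within 0.005. They describe the unadjusted ratio. Neither document gives a figure for the ANCOVA, so the effect of selection has to be simulated.

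**2. Simulation assumptions (not in the documents).** Normal log10 data with SD 0.5 in every arm; baseline/Day 29 correlation 0.5; treatment and baseline forced in; entry/stay p = 0.15. Age and sex are either null or explain 4% of variance each. The fixed model is baseline + age + sex. There were 20,000 runs per row below, giving a Monte Carlo SE of √(0.95 × 0.05 / 20,000) ≈ 0.15 point.

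**3. Coverage and width with age and sex as the only candidates (two-arm model).**

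| Evaluable | Covariates | Stepwise coverage | Fixed coverage | Stepwise half-width | Fixed half-width | Stepwise narrower by |
|---|---|---|---|---|---|---|
| 18:18 | null | 94.7% | 95.3% | 0.2933 | 0.3056 | 4.0% |
| 18:18 | informative | 93.9% | 94.6% | 0.2828 | 0.2893 | 2.2% |
| 36:18 | null | 94.8% | 95.1% | 0.2510 | 0.2577 | 2.6% |
| 36:18 | informative | 94.6% | 95.1% | 0.2409 | 0.2433 | 1.0% |
| 72:36 | null | 94.8% | 94.9% | 0.1753 | 0.1774 | 1.2% |
| 72:36 | informative | 94.7% | 94.9% | 0.1675 | 0.1677 | 0.1% |

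Around a ratio of 0.75 at 18:18 with informative covariates, the half-widths give about (0.39, 1.44) stepwise and (0.39, 1.46) fixed. In the null case at 18:18, a baseline-only model has half-width 0.2956. Most of the 4.0% gap there is therefore the price of fitting two useless covariates, not a selection artefact.

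With entry/stay p = 0.05 and informative covariates, coverage at 18:18 is 94.0%. One four-arm model with two candidates gives 94.3–95.3% at the interim.

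**4. If the open list grows.** Six baseline characteristics are listed in SAP section 4.6.4, and randomisation is blocked by site, so six to eight candidates is conceivable. Six candidates (two prognostic) gave 93.1% at 18:18 in 1,500 runs. Eight null candidates gave 93.0% at 18:18 and 92.8% at 36:18. A four-arm model with eight gave 93.2–93.9% at the interim and 93.3–94.3% at full size (2,500 runs, SE about 0.4 point).

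**5. Stability of the model.** With two null candidates, the chance of selecting at least one is about 1 − 0.85² = 28%, which the simulation matched. If selection is repeated over 52 outcomes, 52 × 0.2775 ≈ 14 outcomes would be expected to pick up a covariate by chance. With two modest covariates at 18:18, the four possible models were chosen 28%, 25%, 24% and 22% of the time. In a four-arm model (18/27/36/18 at the interim, 36/54/72/36 at the final), the interim and final models for the same outcome differed in about 31% of runs with two candidates and 77% with eight.

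**6. Where the precision gain comes from.** Baseline adjustment scales the log-scale width by about √(1 − ρ²). For assumed ρ of 0.3, 0.5 and 0.7 the factors are 0.954, 0.866 and 0.714, so 0.36–1.58 becomes about 0.37–1.52, 0.39–1.43 or 0.44–1.27. Baseline is already a fixed covariate, so dropping stepwise selection neither creates nor removes this gain.

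**The case against.** The case for leaving the text alone is fairly strong. All analyses are descriptive. An unadjusted ratio, computed the same way for every serotype and untouched by selection, comes first in section 4.6.6, and the precision tables are built on it. The adjusted ratio reads as an addition, and nothing ties the exclusion of formulations to it. All of this stands and limits the importance of the point. It does not justify a data-driven model where a fixed one is just as easy.

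A reader might infer four stronger things that the documents do not support.

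- **That the intervals are materially too narrow.** With the two named covariates the shortfall is about 1 point at worst. Larger losses need a longer list that the SAP does not give.
- **That adjusted ratios with different covariates cannot be compared.** Treatment is randomised and the model is linear on the log scale, so each fit targets the same mean log difference. Changing covariates adds noise and alters precision, not the quantity estimated. The three formulations would also share covariates if one four-arm model is fitted per outcome, which the wording allows.
- **That the adjusted ratio must be the headline.** The estimand in SAP Table 2 is a ratio of GMCs or GMTs, with no mention of adjustment. The gain in step 6 rests on assumed correlations.
- **That the sponsor would choose covariates after seeing results.** An independent CRO team runs the interim analysis, participant IDs are masked, and nothing gives the sponsor that choice.

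The SAP also does not expressly say that selection is repeated for each outcome. That is the natural reading, but the silence is part of the gap.

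**Conclusion.** The point holds as a weakness of pre-specification and consistency, with a small effect on interval coverage. As written, the adjusted model can vary between outcomes and between the interim and final analyses of the same outcome, and its CI takes no account of the selection.

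Under-coverage is at most about 1 point at interim sizes with age and sex, about 0.3 point at full size, and about 2 points at interim sizes only with six to eight candidates. These sizes depend on the assumed entry/stay level, baseline correlation and covariate effects, none of which the documents state. The frequency of model changes also assumes that selection is repeated for each outcome. The separate gap, that neither ratio is designated for the forest plots, follows from the text alone.

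**What to change.** In SAP section 4.6.6, remove the open-ended wording and the reference to stepwise selection. State that the same ANCOVA is fitted for every serotype, assay and analysis, with treatment group, log-transformed baseline response, age (continuous) and sex.

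State in advance whether the forest plots show the unadjusted or the adjusted ratio. The baseline-adjusted ratio is a reasonable choice for precision, but the documents do not require it.

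The cost is a sentence or two in the SAP and two degrees of freedom. Intervals become about 2–4% wider than stepwise at 18:18 and about 1% or less at 72:36. Programming becomes simpler.
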